# Aim and Hypothesis

The primary aim of this study is to conduct a three-group randomized, intervention trial to measure the effectiveness of the values-framed individually tailored messaging Vaccines and Your Baby (VAYB) intervention. The primary hypothesis to be tested is that infants of mothers who receive the VAYB intervention will be more up to date on vaccination and mothers will have lower levels of vaccine hesitancy than those receiving an untailored version of the intervention or those receiving usual care. A secondary aim of the project is to assess the impact of the intervention on vaccination attitudes.

#### **Methods**

Study Design

This study includes longitudinal follow-up for a 3-armed, individually randomized clinical trial.

Study arms include:

- 1) the tailored (VAYB) intervention
- 2) an untailored version of the intervention (untailored)
- 3) usual care (UC).

Study Setting

Kaiser Permanente Colorado (KPCO) is a nonprofit, managed care organization. There are approximately 667,000 member with approximately 5,000 pregnancies annually and 140,000 children receiving care at KPCO clinics.

Study Population and Inclusion/Exclusion Criteria

# Inclusion

- 1. Currently enrolled at KPCO
- 2. Plan to use KPCO medical care for their child
- 3. English speaking
- 4. >18 years of age
- 5. Last trimester of pregnancy, based on clinically determined expected delivery date

#### **Exclusion Criteria**

- Any of the following conditions confirmed in the electronic medical record (EMR) or patient report
  - a. fetus has a high-risk condition (e.g., fatal heart condition, trisomy 18, anencephaly),
  - b. spontaneous or elective abortion
  - c. social issues (such as domestic violence)
  - d. serious health concerns for the mother

Participants are screened for eligibility using the (EMR). Chart reviews are conducted on patients with health indicators of exclusion criteria in the EMR. If exclusion criteria are confirmed, participants are not recruited for the study.

Study participants can enroll from the first recruitment outreach that occurs in the last trimester of pregnancy to when their infant is  $\leq 2$  months of age. Participants are removed from the study if they have a fetal demise, infant death, if the infant loses KPCO insurance coverage for greater than 90 days, if they request to be removed from the study or if they die. This data is obtained from a monthly data extraction from the EMR and patient report.

#### Consent and Recruitment

Eligible participants are sent a series of 2 letters, 3 emails, and one phone call 1-2 weeks apart. Participants are directed to the KPCO study registration website created specifically for this study. On this registration website the participants identity and eligibility are confirmed, and consent is electronically signed.

After consent, participants are directed to the *study* website where they set up login information and are provided with a Baseline Questionnaire.

The following topic areas are assessed in the Baseline Questionnaire:

- 1. intention to vaccinate
- 2. vaccination values
- 3. logistical barriers to vaccination

- 4. vaccine attitudes and beliefs (vaccination concerns)
- 5. vaccine hesitancy (used for randomization)
- 6. demographics.

Upon completion of this questionnaire, participants are considered to be "enrolled" in the study and are randomized.

#### Randomization

Participants are randomized using stratified randomization along with permuted block technique using a 1:1:1 allocation ratio between the VAYB, untailored and usual care arms. Randomization occurs using software embedded in the study website immediately following enrollment into the study. Randomization remains in place throughout the study. Participants are first stratified into either a hesitant or non-hesitant group, based on vaccine hesitancy status from the baseline questionnaire. Hesitancy status is assessed using a 5-item validated measure developed by Opel DJ (olejado). Participants are categorized based on the measure's suggested (but unpublished) cutoffs. Participants from each group are then added to their own set of blocks that each contain 6 slots. There are 2 slots available for each of the 3 study arms. These slots are randomly ordered when the block is created. When all 6 slots are filled, a new block with 6 randomly ordered slots is added.

# Blinding

During the consent process, study arms are described to the participant. So, while participants are not explicitly informed about which study arm they are assigned to, they are not blinded to their study arm assignment. The project manager for the study is the only unblinded team member during analysis and data interpretation. She converts study data to unlabeled arms (i.e. arm 1, 2 or 3) allowing for the rest of the study team to be blinded to study arm assignment. Unblinding occurs after primary study outcome analysis. Clinics where participants receive care are only aware of individual's study participation if mentioned by the patient during a clinical encounter.

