# Child is 13 to 15 months of age

Vaccine hesitancy level is reassessed at a 4th survey and the content is again refreshed. Satisfaction with the study was also assessed at the 13-15 month survey.

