#### **Outcomes**

Primary: Vaccination status

Vaccination data is collected routinely as part of clinical care within the KPCO health system and will be assessed from the KPCO EMR at pre-defined ages (200 days and 489 days). Colorado Immunization Information System (CIIS) will be used as a secondary vaccination data source, though internal audits demonstrate that >95% of childhood vaccines given to KPCO patients are captured within the EMR.

The primary outcome of the study is a dichotomous categorization of vaccination status (up-to-date vs. not up-to-date) that is defined based on a continuous measure of days under-vaccinated. This outcome is assessed at 200 days of age to cover vaccines in the initial infant vaccination series and to minimize the loss to follow-up. The following 6 vaccines recommended by the Advisory Committee on Immunization Practices will be assessed: hepatitis B; rotavirus; diphtheria-tetanus-acellular pertussis; Haemophilus influenzae type b; pneumococcal conjugate vaccine; and polio.

To categorize vaccination status, we will first assess the number of days under-vaccinated for the 2- and 4-month vaccines (combined), by calculating the difference between when a vaccine dose was actually administered and when a vaccine dose should have been administered according to the vaccination schedule recommended by the Advisory Committee on Immunization Practices,² plus an additional 30 day "leeway" to account for vaccination that did not occur at exactly the minimal interval between doses. For example, the first dose of rotavirus vaccine is due at age 2 months (61 days) but is not considered late until age 92 days. Days undervaccinated for this dose begin accruing on day 93. The number of days under-vaccinated is then summed across all doses and vaccines to calculate a total number of days undervaccinated for each infant and can range from 0-648 days. Infants with 0 total days undervaccinated (assessed specifically for the 2 and 4 months vaccines) at 200 days will be considered up-to-date on their vaccination status; those with ≥1 days undervaccinated will be considered not up-to-date.

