## Secondary Outcomes:

# 1. MMR up-to-date status

A secondary vaccination metric that is assessed is up-to-date status for measles-mumps-rubella (MMR) and varicella vaccine at 489 days, when delay for the first dose of these vaccines begins. This metric is useful because it incorporates outcomes related to parents' decision-making about these two vaccines recommended at 12-15 months of age that are not offered previously.

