# 2. Vaccination attitudes and hesitancy

Vaccine attitudes and hesitancy was in a questionnaire online. These data are used to assess changes over time in vaccination attitudes and hesitancy, and how these relate to study arm, vaccination values, and vaccination status. Vaccination attitudes are assessed using measures previously developed by our team and others. vaccine values are assessed using a novel framework we have developed, and vaccine hesitancy is assessed using a 5-item validated measure (Olejado). A variety of covariates and potential moderators will be assessed as part of this analysis including parent age, gender and insurance coverage type (such as Medicaid and HMO), and mother's age, race, and ethnicity. Also included will be metrics measuring website engagement (VAYB and Untailored arms only) including time spent on the website, number of times viewing website, number and order of pages viewed, and match between stated concerns and website material viewed (VAYB arm only).

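### The analyst blind is guaranteed only through the 200-day analysis, so the survey comparisons, whose models are still open, may be run with arms known

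*Combined protocol and SAP*

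**What the plan says.** The Blinding section makes three statements that bear on this point.

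- Who knows the arms: "The project manager for the study is the only unblinded team member during analysis and data interpretation". This is not limited to any one outcome.
- How the others are masked: the project manager replaces arm names with the numbers 1, 2 and 3. No other masking is described.
- When it ends: "Unblinding occurs after primary study outcome analysis".

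The Outcomes section defines the primary outcome as up-to-date vaccination status: "This outcome is assessed at 200 days of age to cover vaccines in the initial infant vaccination series". The first secondary outcome is "up-to-date status for measles-mumps-rubella (MMR) and varicella vaccine at 489 days". The second is vaccination attitudes and hesitancy, taken from questionnaires. The last of these comes when the child is 13 to 15 months old: "Vaccine hesitancy level is reassessed at a 4 th survey". The Aim and Hypothesis section nevertheless puts lower maternal hesitancy in the primary hypothesis, beside infant vaccination.

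Under the second secondary outcome, the plan lists website engagement metrics for the VAYB and untailored arms, and one metric for a single arm: "match between stated concerns and website material viewed (VAYB arm only)". The Usual Care section says that this arm has no access to either website.

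**The concern.** The two sentences on unblinding do not fit together. If the first covers all analysis and interpretation, the key should not be released while secondary analyses remain. If release follows the primary analysis, the secondary analyses have no stated blind.

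The assured blind covers an outcome computed by a fixed rule from routine records, where an analyst has little to decide. The survey comparisons leave more to decide. The Analysis section adjusts the mixed models for covariates without a final list. The attitudes section offers a broad set of candidate covariates and moderators. The Missing data section leaves the imputation models to be developed. If those choices are made by someone who can see which arm each option favours, the hesitancy result is open to an analyst bias that the coded arms were meant to prevent.

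**Working it through.** The plan gives no design figure to reproduce. The check compares the sections and uses simple arithmetic on the assessment ages.

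**1. What the blind covers**

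| Analysis | Source | Blind stated to hold? | Choices still open |
|---|---|---|---|
| Vaccination status, 200 days (primary) | EMR, cross-checked with the state registry | Yes | Few: fixed age and rule |
| MMR/varicella status, 489 days | Same | Not stated | Few: fixed age, same rule for absent doses |
| Hesitancy, attitudes, intention | Questionnaires | Not stated | Final covariates, moderators, imputation models |

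**2. Timing of the 489-day outcome**

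Inputs: ages 200 and 489 days (Outcomes; MMR up-to-date status). Assumption: 30.4 days per month.

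- Gap for each infant: 489 − 200 = 289 days; 289 / 30.4 = 9.5 months.
- If the primary analysis is run when the last infant reaches 200 days, complete 489-day data follow about 289 days later.
- If it is run after all follow-up, the gap is 0.

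The plan does not date the primary analysis, so the range is 0 to about 289 days.

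**3. Timing of the surveys**

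- The 10–12 month survey opens at about 10 × 30.4 = 304 days of age.
- The 13–15 month survey opens at about 13 × 30.4 = 395 days and closes at about 15 × 30.4 = 456 days.

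Both windows lie beyond 200 days. With an early primary analysis, the last survey could close up to about 456 − 200 = 256 days after the last infant's primary assessment. With a late one, the gap is again 0.

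**4. Whether the codes can be read from the website data**

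Suppose the website metrics were linked to arms 1, 2 and 3.

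- The arm with no engagement data is usual care, because it has no website access.
- The arm with the concern-to-content match is VAYB.
- The remaining arm is untailored.

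All three codes are then identified. Engagement data without the match metric would by their presence identify usual care only. The plan does not say whether these fields are kept apart from the coded file before unblinding.

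**The case against.** The strongest reply is that the plan is silent on the order of the secondary analyses, and silence is not a statement that they are unblinded. A reader might infer that a team that knows the arms will analyse the 489-day and survey outcomes. The documents do not say so. The sentence about the project manager can be read as covering every analysis, and 200 and 489 days are infant ages, not analysis dates. This stands, and it is why the point is about what the plan permits.

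Other parts of the reply also stand.

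- The 489-day outcome comes from records at a fixed age, with a stated rule for absent doses, so knowing the arms could change little.
- A reader might infer that the website metrics already break the code. They are listed for the attitudes and hesitancy work, not for the vaccination analyses, and nothing says that analysts receive them with coded arms. Analyses using metrics that exist in only one or two arms have to know the arms, so running those after unblinding is consistent with the plan.
- The survey windows are fixed and imputation has a 10% trigger, so choice of time points is not a serious opening.
- Coding the arms for analysts does nothing about mothers who know their arm and report their own attitudes.

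What the reply does not remove is the conflict between the two sentences, or the open covariates and imputation models. Guaranteeing the blind for the primary analysis alone is a defensible choice where hesitancy is peripheral. Here it is part of the primary hypothesis.

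**Conclusion.** The point holds as a gap in a stated rule. Analyst blinding is assured through the 200-day analysis only. The hesitancy, attitude and intention comparisons may be run with arms known while their models are still being settled. The same is possible, with much less consequence, for the 489-day outcome. The period at issue is 0 to about 289 days and depends on an undated primary analysis. It measures opportunity, not bias, and the documents give no basis for estimating a bias. Identification of the arms through website data is conditional on early linkage. The 200-day result, the sample size and the error rate are not affected. This is an inexpensive improvement, worth making because half of the primary hypothesis rests on the survey data.

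**What to change.** Amend the Blinding section as follows.

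1. Release the arm key only when the 200-day, 489-day and survey comparisons between arms are final. Reword the sentence on who is unblinded during analysis to match.
2. If 200-day results must be reported sooner, lock the survey analysis code, covariate list and imputation models, with a date, before the key is released.
3. Have the project manager hold the engagement and match data in a separate file until the arm comparisons are final or, under step 2, locked. Run the analyses that use these data last and label them unblinded.

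The cost is a few sentences and one extra data file, with no change to sample size, error rate or participant procedures. The engagement analyses would start later, and an early 200-day report would need either coded arms or a prior lock of the secondary analysis code.

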#### Interventions

#### Tailored Intervention

The VAYB intervention website contains content tailored to participants based on survey responses on the following topic areas:

- 1. intention to vaccinate
- 2. personal attitudes and beliefs about vaccines (vaccination concerns)
- 3. vaccination values
- 4. logistical barriers to vaccination
- 5. child's nickname and age (collected by the study team through birth date information from the EMR).

The most highly tailored content is in three "Just for You" tiles that are displayed prominently on the landing page. These tiles reflect the three vaccine concerns participants indicated they would like more information about. The tiles were further customized on vaccine values, vaccine intention and personal characteristics. The remaining content is lightly tailored to reflect

participant's personal characteristics and vaccine intention. Topic areas highlighted on the home page further identifies additional vaccination concerns identified by participants' survey responses.

The website tailoring on participant's vaccination concerns, values and hesitancy is refreshed 3 times during the course of the study; when the child is 4-6 months, 10-12 months, and 13-15 months of age when the child receives vaccinations.

## Child is 4 to 6 months of age

Participants re-answer all questions excluding the value items, and 2 of the 5 questions assessing vaccine hesitancy. The website tailored content is refreshed accordingly.

## Child is 10 to 12 months of age

All questions, including values are reassessed again in the 3rd survey. The website tailored content is refreshed accordingly.

# Child is 13 to 15 months of age

Vaccine hesitancy level is reassessed at a 4th survey and the content is again refreshed. Satisfaction with the study was also assessed at the 13-15 month survey.

#### Untailored Intervention

The untailored intervention has the same text, content and design as the VAYB intervention, However, it does not contain any content tailoring linked to survey responses. The same questionnaires administered to participants in the VAYB arm are administered to participants in the untailored arm (baseline, and when the child is 4-6 months, 10-12 months, and 13-15 months of age), but the material is not used to tailor the website content.

## **Usual Care**

After taking the Baseline Questionnaire, participants in the usual care arm are thanked for their time and logged off the study website. They receive an email containing the Vaccine Information Statements (VIS) for the vaccines due in the child's first year of life. They do not have access to the VAYB or untailored websites.

#### All arms

Routine pediatric care is available to infants of all participants in the study. At KPCO this typically consists of a series well-child care visits at 2 weeks, 2 months, 4 months, 6 months, and 12 months of age, with an optional visit at 9 months of age if desired by the healthcare provider or parent. Well child visit content is based on the Bright Futures program of American Academy of Pediatrics guidelines. The visit content is focused on the needs of the child and family that typically last 20 minutes or less. Parents are provided with the VIS relevant to that visit. Providers are often asked about vaccination and can provide additional information verbally.

Vaccination intention: For all time points, vaccination intention is assessed in the survey. Vaccination intention is assessed again following exposure to the intervention, or in the case of usual care after completing the survey. Post intervention vaccination intention is obtained through an emailed survey sent within an hour of completing the survey. A reminder for this vaccination intention assessment is sent to non-responders by email after one day.

Participants receive a \$20 gift card after surveys at each timepoint (baseline, and when the child is 4-6 months, 10-12 months, and 13-15 months of age) are complete.

#### **Outcomes**

Primary: Vaccination status

Vaccination data is collected routinely as part of clinical care within the KPCO health system and will be assessed from the KPCO EMR at pre-defined ages (200 days and 489 days). Colorado Immunization Information System (CIIS) will be used as a secondary vaccination data source, though internal audits demonstrate that >95% of childhood vaccines given to KPCO patients are captured within the EMR.

The primary outcome of the study is a dichotomous categorization of vaccination status (up-to-date vs. not up-to-date) that is defined based on a continuous measure of days under-vaccinated. This outcome is assessed at 200 days of age to cover vaccines in the initial infant vaccination series and to minimize the loss to follow-up. The following 6 vaccines recommended by the Advisory Committee on Immunization Practices will be assessed: hepatitis B; rotavirus; diphtheria-tetanus-acellular pertussis; Haemophilus influenzae type b; pneumococcal conjugate vaccine; and polio.

To categorize vaccination status, we will first assess the number of days under-vaccinated for the 2- and 4-month vaccines (combined), by calculating the difference between when a vaccine dose was actually administered and when a vaccine dose should have been administered according to the vaccination schedule recommended by the Advisory Committee on Immunization Practices,² plus an additional 30 day "leeway" to account for vaccination that did not occur at exactly the minimal interval between doses. For example, the first dose of rotavirus vaccine is due at age 2 months (61 days) but is not considered late until age 92 days. Days undervaccinated for this dose begin accruing on day 93. The number of days under-vaccinated is then summed across all doses and vaccines to calculate a total number of days undervaccinated for each infant and can range from 0-648 days. Infants with 0 total days undervaccinated (assessed specifically for the 2 and 4 months vaccines) at 200 days will be considered up-to-date on their vaccination status; those with ≥1 days undervaccinated will be considered not up-to-date.

## Secondary Outcomes:

# 1. MMR up-to-date status

A secondary vaccination metric that is assessed is up-to-date status for measles-mumps-rubella (MMR) and varicella vaccine at 489 days, when delay for the first dose of these vaccines begins. This metric is useful because it incorporates outcomes related to parents' decision-making about these two vaccines recommended at 12-15 months of age that are not offered previously.

# 2. Vaccination attitudes and hesitancy

Vaccine attitudes and hesitancy was in a questionnaire online. These data are used to assess changes over time in vaccination attitudes and hesitancy, and how these relate to study arm, vaccination values, and vaccination status. Vaccination attitudes are assessed using measures previously developed by our team and others. vaccine values are assessed using a novel framework we have developed, and vaccine hesitancy is assessed using a 5-item validated measure (Olejado). A variety of covariates and potential moderators will be assessed as part of this analysis including parent age, gender and insurance coverage type (such as Medicaid and HMO), and mother's age, race, and ethnicity. Also included will be metrics measuring website engagement (VAYB and Untailored arms only) including time spent on the website, number of times viewing website, number and order of pages viewed, and match between stated concerns and website material viewed (VAYB arm only).

